4.4. Subject Withdrawal or Termination

4.4.1. *Reasons for Withdrawal or Termination*

Subjects may withdraw from participation in the study at any time upon request.

The Investigator may choose to terminate participation of the subject from the study with or without their consent for any of the following reasons:

- Adverse events
- Noncompliance
- For any reason that may, in the opinion of the Investigator, negatively affect the safety or well-being of the subject.

An Investigator must terminate participation of a subject from the study for any of the reasons indicated in section 4.15.

4.4.2. *Handling of Withdrawal or Termination*

Every effort should be made to assess SSCs and adverse events prior to the subject withdrawal. If a subject does not return for a scheduled visit, every effort should be made to contact the subject.

For subjects who are lost to follow-up, the Investigator will make attempts to collect at least the vital status (e.g., whether the subject is alive) before formally withdrawing the subject from the study. Prior to considering a subject lost to follow-up at least two documented attempts should be made to contact the subject through all available routes, and a certified letter should be sent to the permanent address on file.

Once the subject withdraws from the study, no further study evaluations will be performed, and no additional data will be collected. The Investigator may retain and continue to use any data collected before withdrawal. The subject will not be replaced.

If for any reason the subject is withdrawn by the Investigator from this study, the Investigator will inform the subject and KCI.

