3.2. Design Summary

This post-market, prospective, randomized, open-label, multicenter, controlled study will evaluate the effectiveness of closed incision negative pressure therapy (ciNPT) compared to standard of care (SOC) surgical dressing in reducing the surgical site complications (SSCs) in subjects with revision of a failed total knee arthroplasty (TKA).

The study will randomize approximately 440 subjects from approximately 15 sites in a 1:1 ratio to receive either ciNPT or SOC after a revision TKA. Subjects randomized to the ciNPT treatment arm will receive the placement of a Prevena™ Dressing in conjunction with ActiV.A.C.® or Prevena Plus™ 125 Therapy Units for a duration consistent with the Instructions for Use (IFU) document for the selected dressing but no shorter than five days post-surgery. Subjects randomized to the SOC treatment arm will receive Aquacel® Ag Surgical incision dressing, or another equivalent silver-impregnated dressing, up to the maximum number of days specified in the IFU but no shorter than five days post-surgery, not inclusive of other negative pressure wound therapy devices or dressings for the duration of the study.

Subjects will be seen during Screening (no more than 30 days before TKA revision) at the TKA revision, at weekly study treatment visits (a minimum of 5 days to a maximum number of days indicated in the Instruction for Use document for the selected dressing), the Midterm Follow-up visit (day 30 to 45), the Long Term Follow-up visit (day 90 to 104), or as initiated by either the Investigator or the subject (Unscheduled). All subjects will be followed for 90 days for outcomes regardless of the treatment received.

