4.16. End of Study

Subjects may withdraw or be discontinued from this study at any time (Section 4.4.1). The Investigator may discontinue a subject's study participation if the Investigator feels it is in the best interest of the subject. Subjects who consent to participate in the study but do not satisfy the inclusion and exclusion criteria will be considered screen failures.

The following information will be documented:

- Date of study termination
- Completion of the study (yes/no)
- Primary reason for discontinuation

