8.3.4. Analysis of Primary Endpoint

The analyses described in this section will be performed for the overall primary endpoint, “Any Surgical Site Complication (SSC)”, within 90 days of TKA revision, and repeated for each type of complication.

The proportion of subjects with each possible result – “Occurred”, “No occurrences”, or “Incomplete follow-up” will be reported, using the mITT Analysis Set as the denominator. See section 8.1.1 for definitions of these outcomes.

The comparative analysis of the primary endpoint will only consider subjects in the mITT Analysis Set, i.e., subjects with “Incomplete Follow-up” will be excluded. The proportions

of subjects with “Occurred” will be calculated within each treatment group and compared between treatment arms using a Cochran-Mantel-Haenszel (CMH) p-value stratified for type of revision (aseptic vs. septic). The difference between the proportions (ciNPT – SOC) and asymptotic 95% confidence interval will be computed. At the final analysis, a two-sided significance level adjusted for the interim efficacy analyses and potential sample size recalculation (e.g., $\alpha = 0.048$ if interim look is at $t=0.50$ and no sample size adjustment is made) will be used to compare the SSC proportions between the two treatment arms.

Supportive/exploratory analyses of the primary efficacy endpoint, SSC, may include:

- analyses comparing the treatment groups for the septic and aseptic revisions;
- analyses comparing the treatment groups for age, BMI, race/ethnicity, material used in the revision, and sex subgroups;
- analyses comparing the heterogeneity of the treatment groups across clinical sites;
- multivariable analyses comparing the treatment groups with covariate adjustment where possible covariates might include (but not limited to) age, BMI, sex, type of revision (aseptic or septic), and subject co-morbidities;
- Fisher’s exact test presenting the unstratified p-value;
- A repeat of any analysis above using the Per-Protocol and/or mPP Analysis Sets;

and other exploratory analyses as deemed appropriate.

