8.4.2. Sample Size Determination

The primary endpoint of this study is the subject incidence of SSC as defined in section 4.11.1. The incidence rates of SSC are different for septic and aseptic revisions; the assumed SSC rate is 33% for septic and 6.9% for aseptic. This study plans to enroll at least 50% septic revisions overall. These enrollment rates lead to an assumed pooled SSC rate of 20% in the SOC dressing arm.

Assuming an overall type 1 error rate of 0.05, with a two-sided hypothesis test, the study will have at least 80% power to detect a difference of 10% (50% reduction) in SSCs in the ciNPT arm with 199 subjects in each treatment arm, with one interim analysis at about 50% of the evaluable subjects for a total of 398 subjects using the likelihood ratio test. With an estimated 5%-10% loss, a non-binding interim analysis for superiority at approximately 50% of the evaluable subjects using O'Brien-Fleming method for monitoring boundaries, the planned sample size will be inflated for potential loss of follow-up for a total of 440 subjects.

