7.3 Handling of Missing data/Dropouts

In general, missing data will not be imputed except for the followings:

- the date of AEs as described in Section 7.2 of this document

- the data imputation for sensitivity analyses for exploratory endpoints Pain, KOOS scores and PROMIS Global 10 as described in Sections 8.7.1, 8.7.2 and 8.7.3 respectively

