The first test will utilize all subjects from the mITT combined population included in the interim and subjects post-interim. The second test will utilize only the post-interim mITT subjects from either the septic or aseptic population depending on the results and/or decision from the interim analysis. The second test will be performed only if the test 1 is statistically significant at the 0.048 level.

Case 1 Did Not Enrich	Case 2 Enriched with Septic	Case 3 Enriched with Aseptic

 • Test 1: Adaptive test of H_0 (Combined population) 	
 • Test 1: Adaptive test of H_0 (Combined population) • Test 2: standard test of H_0 (post-interim population only) 	
 • Test 1: Adaptive test of H_0 (Combined population) • Test 2: standard test of H_0 (post-interim population only)

For Case 1, if the 2-sided p-value from the test 1 is ≤ 0.048 and the SSC rate of the ciNPT arm is lower than the SSC rate of SOC arm, then the null hypothesis is rejected; superiority in effectiveness of the ciNPT arm compared with the SOC arm will be established. However, for Case 2 or Case 3, both test 1 and test 2 must reject the null hypothesis at the 0.048 level in order to claim statistical significance.

Additionally, figure(s) may be generated to display the results from the analyses of the primary endpoint graphically.

Supportive/exploratory analyses of the primary efficacy endpoint described below in Section 8.5.1 will be performed on the mITT analysis set unless otherwise specified.

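### Discretionary removal from the study (Protocol 4.4.1, 4.16) stops SSC follow-up and drops SSC-free subjects from the primary comparison, contrary to Protocol 3.2; the bias could run either way

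*Protocol*

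**What the plan says.** The study is open-label and the primary endpoint is Investigator-assessed (Protocol 3.2, 3.4).

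- **Removal.** Protocol 4.4.1: "The Investigator may choose to terminate participation of the subject from the study with or without their consent for any of the following reasons". The reasons are adverse events, noncompliance, and anything the Investigator believes may harm the subject's safety or well-being. Protocol 4.16 adds: "The Investigator may discontinue a subject's study participation if the Investigator feels it is in the best interest of the subject".
- **Consequence for data.** Protocol 4.4.2: "Once the subject withdraws from the study, no further study evaluations will be performed, and no additional data will be collected". The subject is not replaced. The same section asks for every effort to assess SSCs before withdrawal.
- **Consequence for analysis.** Protocol 8.1.1 and SAP 4.1 classify a subject with no known SSC and no assessment at or after day 90 as Incomplete follow-up. Protocol 8.3.4: "The comparative analysis of the primary endpoint will only consider subjects in the mITT Analysis Set". That set (Protocol 8.2, SAP 5) keeps anyone with an SSC by day 90, and otherwise requires an assessment on or after day 90. SAP 7.3: "In general, missing data will not be imputed except for the followings". The listed exceptions are AE dates and the pain, KOOS and PROMIS sensitivity analyses, so SSC is not imputed.
- **The contrary statement.** Protocol 3.2, repeated in the synopsis: "All subjects will be followed for 90 days for outcomes regardless of the treatment received".

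**The concern.** The protocol defines no way to stop the study dressing under 4.4.1 or 4.16 and remain in outcome follow-up. The same decision ends both.

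The resulting exclusion is not neutral with respect to outcome. A subject removed after an SSC still counts as an event. A subject removed without one leaves both numerator and denominator, and anything that happens later in the 90 days is never seen. Protocol 4.11.1 notes that some surgical complications reported as adverse events will not meet the SSC criteria. A subject with incision trouble can therefore be removed while still SSC-free.

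The hypothesis in Protocol 8.4.1 concerns the difference in 90-day SSC proportions between the arms. If the later risk of removed subjects differs from that of retained subjects, the comparison instead describes those whom an unblinded Investigator kept in the study plus those who had already had an event. Because no data are collected after removal, the trial could not show afterwards how large the distortion was.

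**Working it through.** **1. The plan's own figures.** Inputs from Protocol 8.4.2: SOC 20%, ciNPT 10%, 80% power, 5% to 10% loss, and "Assuming an overall type 1 error rate of 0.05, with a two-sided hypothesis test".

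- SOC rate: 0.5 × 33% + 0.5 × 6.9% = 19.95%, stated as 20%.
- n per arm = [1.96·√(2 × 0.15 × 0.85) + 0.8416·√(0.20 × 0.80 + 0.10 × 0.90)]² / 0.10² = (0.990 + 0.421)² / 0.01 = 199. This matches the plan.
- Inflation: 398/0.95 = 419 and 398/0.90 = 443; the plan uses 440. Planned loss is therefore 22 to 44 of 440 subjects.

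The required 199 per arm is unaffected by this point. What changes is who is counted.

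**2. Bias formula.** Let p be an arm's true 90-day SSC rate, w the share removed SSC-free, and r their unobserved later SSC risk. Then p = (1 − w) × observed + w × r, so

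observed = (p − w·r)/(1 − w).

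The documents give neither w by arm nor r. Setting w to 5% or 10% attributes the whole planned loss to this route, which is an upper-end assumption. The value r = 33% borrows the plan's septic rate.

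**3. Results at true rates of 20% and 10%.**

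| Assumption | w | SOC observed | ciNPT observed | Difference (points) | Against 10 points |
|---|---|---|---|---|---|
| Both arms, r = 33% in each | 5% | 19.3% | 8.8% | 10.5 | +5% |
| | 10% | 18.6% | 7.4% | 11.1 | +11% |
| ciNPT only, r = 33% | 5% | 20.0% | 8.8% | 11.2 | +12% |
| | 10% | 20.0% | 7.4% | 12.6 | +26% |
| ciNPT only, r = 10% | 5% or 10% | 20.0% | 10.0% | 10.0 | 0 |
| Both arms, r = twice own rate (40%, 20%) | 5% | 18.9% | 9.5% | 9.5 | −5% |
| | 10% | 17.8% | 8.9% | 8.9 | −11% |

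Example, ciNPT at w = 5%, r = 33%: (0.10 − 0.05 × 0.33)/0.95 = 0.0835/0.95 = 8.8%.

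Two patterns explain the table. With equal w and equal r in both arms, r cancels and the difference is 10/(1 − w) points: 10.5 or 11.1. With r equal to twice each arm's own rate, the difference is multiplied by (1 − 2w)/(1 − w): 0.947 or 0.889. The sign of the bias therefore depends on how later risk relates to arm.

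**4. No true effect (20% in both arms), r = 33%.** Final level 0.048 two-sided (SAP 8.5, "only if the test 1 is statistically significant at the 0.048 level"), that is 0.024 in favour of ciNPT; 220 per arm before removal; single-look normal approximation.

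- Equal removal, equal r: the chance of a false ciNPT win stays at 2.4%.
- ciNPT removal of 5% or 10%, SOC at half that share: 3.0% or 3.7%.
- Removal in ciNPT only, 5% or 10%: 3.6% or 5.4%.

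With the arms reversed, the shift runs against ciNPT.

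**5. Can the planned loss overturn a result?** Take 10% loss per arm and design rates among completers: 40/198 against 20/198, p = 0.005 (unstratified, single look). Add back the 22 excluded per arm.

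- No later SSCs among excluded SOC subjects and 6 of 22 among excluded ciNPT subjects: 40/220 against 26/220, p = 0.062, above 0.048. With 5 of 22, p = 0.044.
- 4 of 22 SOC and 9 of 22 ciNPT: 44/220 against 29/220, p = 0.055.

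It can, but only if excluded ciNPT subjects do clearly worse than excluded SOC subjects.

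**The case against.** **It is a permission, not an event.** Section 4.4.1 says the Investigator may terminate, and no frequency is given. Section 3.2 points to keeping such subjects. Noncompliance also has its own route: disqualifying deviations remove a subject from the Per-Protocol set, not from mITT. This stands in part. It makes the size unknowable, but it does not resolve the conflict. The heading of 4.4.2 covers termination as well as withdrawal, and the visit schedule provides an End of Study assessment for subjects who discontinue before the 90-day visit.

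**A reader might infer that the bias favours ciNPT.** Protocol 6 lists incision-site risks for the ciNPT system, and a powered unit might seem to invite more noncompliance. The documents do not support that step. Section 6 covers only the ciNPT devices and dressings, with no SOC list to compare. No section says that noncompliance differs by arm. Some of the listed risks, such as localized infection or surgical site disruption, could themselves meet an SSC definition, and those subjects would stay in the analysis as events.

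**The larger figures are near worst case.** The 12% to 26% range puts the whole planned loss on one route and one arm, and uses a full 90-day rate as the later risk although part of the risk period has passed. This stands, so those figures are an extreme and not an expectation.

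**There are mitigations.** The pre-withdrawal SSC check captures nothing later. The CMH test on the ITT set (SAP 8.5.1) sits among analyses that may be performed and has no rule for unknown outcomes. The time-to-SSC analysis (SAP 8.7.6) is exploratory, and its censoring assumes that removal is non-informative. Tabulating Incomplete follow-up by arm, and the reasons for discontinuation and mITT exclusion (SAP 8.1, 8.5), would reveal an imbalance but not correct it.

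**Conclusion.** The concern holds as an internal conflict with a possible effect on the primary comparison. Sections 4.4.1, 4.4.2 and 4.16 permit what 3.2 rules out, and the exclusion falls only on SSC-free subjects.

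Size and direction cannot be determined from the documents. Under assumed removal of 5% to 10%, the 10-point effect could be overstated by 5% to 11% (both arms, later risk 33% in each), overstated by up to 12% to 26% (ciNPT only, later risk 33%), unbiased (ciNPT only, later risk 10%), or understated by 5% to 11% (both arms, later risk twice the arm's own rate). If only 2.5% were removed, in ciNPT alone at 33% later risk, the overstatement would be 6%.

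The claim that the plan favours ciNPT, or that outcome-related removals will occur, goes beyond the text. The point is worth correcting because the repair is cheap and, without it, the trial's own data could not settle the question.

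**What to change.** Reconcile Protocol 4.4.1, 4.4.2 and 4.16 with 3.2:

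- State that when the Investigator ends a subject's participation on the discretionary grounds of 4.4.1 or 4.16, the already scheduled SSC assessments continue through the Long Term Follow-up visit, unless the subject withdraws consent or cannot be followed.
- State that these subjects count in the mITT set by randomised arm. The set's definition need not change, because a day-90 assessment or an observed SSC already qualifies them.
- Record the reason and date of treatment discontinuation separately from study withdrawal.

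This concerns outcome follow-up only. It leaves the clinical grounds for stopping treatment, including the well-being ground, and the separate mandatory withdrawals in 4.15 unchanged.

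The cost is a short amendment and one eCRF field. The visits are already scheduled and no extra subjects are needed. The downside is some added retention effort and a possibly less favourable estimate. Subjects who still cannot be followed remain excluded as now.

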4.5. Demographics and Subject Characteristics

The following demographic data and subject characteristics will be collected and documented after the subject signs the informed consent and before the TKA revision:

- Date of birth
- Sex
- Race
- Ethnicity
- Co-morbidities
- Primary TKA characteristics
- Date of surgery
- Diagnosis (osteoarthritis, rheumatoid arthritis, other)
- Unilateral or bilateral
- Primary reason for failure
- Aseptic loosening
- Infection
- Wear
- Mechanical causes

- Instability
- TKA revision septic/aseptic

4.6. Vital Signs

The subject's height and weight will be collected and documented at the screening visit. If the screening visit and the TKA revision occur on different days, only weight will be taken and documented on Day 0, prior to the revision procedure.

4.7. Medical/Surgical History

As part of screening procedures, the Investigator, or medically licensed sub-investigator, will collect a complete medical and surgical history for each subject. If the screening visit and the TKA revision occur on different days, the medical and surgical history will be updated on Day 0, prior to the revision procedure.

4.8. Laboratory Assessment for Pregnancy

Serum or urine hCG assessment to determine pregnancy status in female subjects of child-bearing potential will be conducted during screening and prior to surgery, if the screening visit and the TKA revision occur on different days. If the subject's pregnancy test is positive, she will not be eligible for randomization, will discontinue from the study, and will be considered a screen failure.

4.9. Randomization and Subject Numbering

Subjects who sign an informed consent will be assigned a unique subject identifier. The identifier will be unique to the subject. Study data will be reported according to this unique subject identifier.

Subjects who satisfy all inclusion criteria and none of the exclusion criteria will be eligible for randomization which will occur in the operating room after the TKA revision procedure has been completed and the surgical incision has been closed. Randomization to study treatment will be centralized, electronic, and web-based. Subjects will be randomized in a 1:1 ratio (ciNPT vs. SOC) stratified by type of revision (septic vs. aseptic). For details, see section 8.4.3.

If a screened subject does not meet inclusion criteria or meets any exclusion criteria, the subject will not be randomized and will be considered a screen failure.

4.10. Surgical Procedures and Assessments

4.10.1. TKA Revision Procedure

The surgical procedure will be performed in accordance with the Investigator's standard practice and the resultant surgical incision will be closed with sutures (resorbable or permanent) or staples. Incisional skin glue (e.g., Dermabond) must not be used.

The following information regarding the TKA revision will be documented after the surgery:

- Material used (polyethylene, cross-linked polyethylene, antioxidant polyethylene)
- Location (left or right knee)
- Length of the incision
- Method of closure (sutures or staples)
- Start and stop time of the surgical procedure

4.10.2. Application of Study Treatments

4.10.2.1. ciNPT

Subjects randomized to ciNPT will receive treatment for a duration consistent with the IFU document included with the selected Prevena™ Dressing but no shorter than five days post-surgery. Depending on the length of the incision, an appropriate Prevena™ Dressing will be used to cover the closed surgical incision, according to the instructions for use included with the product. Total treatment time should not exceed the maximum number days indicated in the IFU document included with the Prevena™ Dressing applied immediately following surgery.

For the delivery of negative pressure, an ActiV.A.C.® or Prevena Plus™ 125 Therapy Unit will be attached to the dressing tubing and ciNPT will be initiated in the operating room. The ActiV.A.C.® Unit must be set to 125mmHg of continuous negative pressure. If the dressing leaks and a seal cannot be maintained, replacement of the initial ciNPT dressing is acceptable and will be documented.

In the event that the Therapy Unit malfunctions, a replacement unit may be used. A dressing may also be replaced during the treatment period.

4.10.2.2. *Standard of Care (SOC)*

Subjects randomized to standard of care will have their closed surgical incision covered with the silver-impregnated dressing, Aquacel[®] Ag Surgical or other equivalent, up to the maximum number of days specified in the IFU but no shorter than five days post-surgery. Total treatment time should not exceed the maximum number days indicated in the IFU document included with the dressing applied immediately following surgery.

4.10.2.3. *Documentation*

The following information regarding the application of study treatments will be documented after the surgery:

- SOC
- Type of dressing applied
- ciNPT
 - Type of dressing applied (eg, Prevena Plus[™] Customizable[™] Dressing, Prevena[™] Peel & Place[™] Dressing)
- Type of therapy unit
 - ActiV.A.C.[®]
 - Prevena Plus[™] 125
- Replacement of the initial dressing to maintain the seal

4.10.3. **Removal of Study Treatments**

4.10.3.1. *ciNPT*

All subjects must receive ciNPT for a duration consistent with the IFU document included with the selected Prevena[™] Dressing but no shorter than five days post-surgery. A maximum duration indicated in the IFU document of the Prevena[™] Dressing applied immediately following surgery is encouraged. The dressing should not be lifted or removed for reasons other than those related to the device such as initial malfunction or leak alarm.

At the end of the ciNPT treatment period, the dressing and unit are to be removed; re-application of the Prevena[™] dressing is prohibited after the treatment period. If continued drainage is determined by the Investigator's visual inspection of the incision at the time of dressing removal, an SSC event should be documented.

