4.10.3.2. Standard of Care Dressing

The Aquacel® Ag Surgical or other equivalent dressing may be replaced as needed for the duration of the treatment period. Total treatment time should be no shorter than five days post-surgery and should not exceed the maximum number days indicated in the IFU document included with the dressing applied immediately following surgery.

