4.10.3.3. Documentation

The following information regarding the application of study treatments will be documented after the surgery:

- Date of removal
- SOC only
- The number of dressing replacements
- Type of dressing (if any) applied after removal of study treatment
- ciNPT only
- Replacement of therapy unit
- Number and dates of dressing replacements (Prevena™ Peel & Place™ or Prevena Plus™ Customizable™)
- Type of dressing (if any) applied after removal of ciNPT

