4.11. Post-Operative Assessments

4.11.1. Investigator-Assessed Surgical Site Complication (SSC)

The Investigator will examine the subject and the surgical incision at the scheduled assessment visits – Weekly, Midterm Follow-up, and Long Term Follow-up – as well as any unscheduled visits initiated by the subject or the Investigator. The Investigator will evaluate the subject for all complications at each visit, regardless if the subject has a documented SSC event.

For all SSC events, the date of onset will be recorded. Not all reported adverse events that are surgical complications will meet the criteria for an SSC event.

Subjects with a documented SSC event will continue to be assessed through the Long Term Follow-up visit or study withdrawal and all newly occurring complications will be recorded.

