5.2.7. Unscheduled Visits

Outside of scheduled study visits, if the subject needs to be assessed by the Investigator for any reason, the following procedures and assessments will be performed and documented.

- SSC Assessment
- Intervention Assessment
- Healthcare Utilization Assessment
- Concomitant Medications
- AE Assessment and SAE Reporting
- End of Study (only when a subject discontinues prior to the 90-day visit)

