6. RISKS ASSOCIATED WITH STUDY PARTICIPATION

The following are the risks associated with the devices and dressings used in this study, specifically, ActiV.A.C.® Therapy Unit, Prevena Plus™ 125 Therapy Unit, and Prevena™ Dressings.

Risks	Disorders/Conditions
Skin and Subcutaneous Tissue	
 • Epidermal (skin) stripping. • Contusion (bruising) • Local cutaneous reaction (i.e., redness, rash, significant pruritis, urticaria) • Maceration • Minor soft tissue damage • Minor bleeding • Pain
Other	
 • Allergic reaction • Bleeding complications (associated with the surgical procedure, concomitant therapies and co-morbidities) • Increased risk of bleeding from the incision associated with the use of anticoagulants and/or platelet aggregation inhibitors • Deterioration of the wound (due to lack of visibility of incision site through dressing) • Exposure related infection • First degree burn (if device gets warm) • Localized infection • Minor desiccation (due to dressing leak) • Moderate soft tissue damage (i.e., due to trip hazard, tubing entanglement) • Physical discomfort • Surgical Site disruption

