8.7.7 Duration of Treatment and Number of Dressing Changes Analysis

Duration of Treatment: defined as the time in day(s) from the date of TKA revision to the end of treatment and is calculated as:

DOT= (Date of end of treatment – Date of the TKA revision)

Subjects who have their end of treatment on the same day of TKA revision after receiving initial dressing application will be considered to have a duration of treatment of 0.5 days. If subjects did not receive the initial dressing application, then the duration of treatment will be 0 days.

Treatment duration and number of dressing changes will be calculated and summarized by treatment arm, and then will be compared using a 2-sample t-test or Wilcoxon Rank-Sum test as appropriate.

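### The protocol calls for the incision to be examined at every unscheduled visit, but states no exception letting the ciNPT dressing be lifted for a suspected complication

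*Protocol*

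**What the plan says.** **ciNPT dressing.** Protocol 4.10.3.1 sets a minimum of five days of therapy and then says: "The dressing should not be lifted or removed for reasons other than those related to the device such as initial malfunction or leak alarm." Protocol 4.10.2.1, after text on leaks and unit malfunction, adds: "A dressing may also be replaced during the treatment period."

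**SOC dressing.** Under Protocol 4.10.3.2 the silver "dressing may be replaced as needed for the duration of the treatment period."

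**Examination.** Protocol 4.11.1 has the Investigator examine the incision at the scheduled assessments "as well as any unscheduled visits initiated by the subject or the Investigator", and look for all complications each time. Protocol 5.2.7 lists an SSC assessment at an unscheduled visit, which takes place "if the subject needs to be assessed by the Investigator for any reason."

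**Acknowledged risk.** The device risks in Protocol section 6 include "Deterioration of the wound (due to lack of visibility of incision site through dressing".

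**Records and summaries.** For ciNPT, Protocol 4.10.3.3 lists "Number and dates of dressing replacements". For SOC it lists only how many replacements were made. SAP 8.7.7 plans that "Treatment duration and number of dressing changes will be calculated and summarized by treatment arm", followed by a between-arm test. SAP 8.7.9 plans to report reasons for ciNPT replacements.

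**The concern.** A subject on ciNPT may return before planned removal with pain, fever or suspected bleeding. One section tells the site to examine the incision. Another tells it to leave the dressing alone unless the device is at fault. A suspected complication is not a device fault, so a site that looks departs from 4.10.3.1 and a site that does not look departs from 4.11.1.

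The first thing at stake is safety. The protocol names hidden deterioration as a risk of this dressing, while its own wording discourages the obvious safeguard.

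The second is even ascertainment. The trial is open-label and the primary endpoint is Investigator-assessed. If SOC incisions can be seen early more readily than ciNPT incisions, early SSCs have unequal chances of being recorded.

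**Working it through.** No arithmetic applies, because the point concerns instructions and not a rate, an alpha or a sample size. The check sets the instructions side by side and looks for an exception.

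**1. Is examination required while the dressing is on?** Yes. Protocol 4.11.1 and 5.2.7 cover unscheduled visits without excluding the treatment period. The schedule in Protocol 5.1 also marks SSC assessment at unscheduled visits.

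**2. Do scheduled visits conflict?** No. Protocol 5.2.4 pairs the treatment-period SSC assessment with dressing removal. The conflict is confined to visits before planned removal.

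**3. Can the incision be examined with the dressing in place?** The risk entry in section 6 implies that it cannot.

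**4. Does any text supply the exception?**

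| Text | What it allows | Why it falls short |
|---|---|---|
| Protocol 4.10.2.1 | Replacing a dressing during treatment | Names no clinical reason and no inspection; 4.10.3.1 then narrows the reasons for lifting |
| Protocol 4.4.1 and 4.16 | Ending participation for adverse events or the subject's interest | Takes the subject off study; under 4.4.2 data collection then stops |
| Protocol 3.2 | 90-day outcome follow-up whatever treatment was received | Supports continued follow-up, but does not permit lifting |
| Protocol 4.11.2 | Recording interventions for an SSC at any visit | Applies once an SSC is recognised |
| Protocol 7.7 and 8.3.7 | Recording action taken for an adverse event; tabulating events that led to treatment or study discontinuation | Foresees early stopping, but gives no rule for inspection |
| Protocol 10.1 | Sponsor does not influence medical care | General statement, not an instruction on dressings |
| SAP 8.7.7 | A duration for treatment that ends on the day of surgery | A counting rule only |

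None of these says that the dressing may be lifted for a suspected SSC and the subject carried on in the study. SAP 2.3 repeats the treatment durations and adds nothing.

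**5. Which way could detection differ?** SOC dressings can be changed as needed and ciNPT dressings are restricted, so any early loss of events would fall on ciNPT and favour it. Several features limit the loss:
- The endpoint is cumulative to 90 days (Protocol 8.1.1).
- Continued drainage is read after dressing removal in both arms (Protocol 4.11.1.1, item 6).
- Dehiscence, necrosis and collections needing drainage are unlikely to resolve unseen.

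What remains is chiefly superficial infection that begins and settles under the dressing. Sizing this would need the rate of early unscheduled visits, the superficial share of SSCs, the fraction that settles unseen, and the corresponding loss under SOC. The documents give none of these.

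**6. Would the planned outputs show it?** Only in part. Onset dates and the Kaplan-Meier curves by arm in SAP 8.7.6 could show an early gap, but not whether it came from inspection or from treatment. The items in Protocol 4.10.3.3 include no reasons for lifting in either arm and no dates for SOC changes. The case report form was not available, and SAP 8.7.9 expects ciNPT reasons that 4.10.3.3 does not list, so that list may be incomplete.

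**The case against.** The strongest reply is that the rule is advisory. Section 4.10.3.1 says *should not*, while the protocol uses *must* or *must not* where it means to bind, as for minimum ciNPT duration and skin glue. Section 4.11.1 says the Investigator *will* examine. Replacement is allowed, and replacing a dressing exposes the incision. Protocol 8.3.7 and SAP 8.7.7 foresee early discontinuation. The instructions for use and the clinician guide, which may cover clinical removal, are not among the documents. A sensible surgeon would look.

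Most of this stands. A reader might infer that sites are forbidden to look; the wording does not go that far. A reader might also infer that the device is being used unsafely; without the instructions for use, that cannot be claimed. What the reply does not supply is a sentence permitting inspection on clinical suspicion with the subject kept on study.

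The reply is also right about bias. SOC dressings *may* be changed, but nothing requires inspection when they are. Superficial infection can also be recorded on the Investigator's diagnosis (Protocol 4.11.1.1). An uneven detection rate is therefore possible, not shown.

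**Conclusion.** The gap is real and minor. Followed as written, 4.10.3.1 discourages inspection of a suspected complication and makes good care a departure from protocol. Whether such a departure would count as disqualifying for the Per-Protocol set is left to the review committee in Protocol 8.2.

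The conclusion rests on the protocol and SAP text alone, and the instructions for use could soften it. The safety argument needs no assumed number. A reader might go further and infer a material inflation of the false-positive rate for ciNPT. The documents do not support that: any figure would depend on an invented share of events settling unseen and on assuming no such loss under SOC. The most that can be said is that the direction would favour ciNPT and the size is probably small. The proposal is a cheap improvement, not the repair of a flaw in the primary analysis.

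**What to change.** 1. Add to Protocol 4.10.3.1: *The dressing may also be lifted or replaced when the Investigator suspects a surgical site complication; the incision is then inspected, an SSC assessment recorded, and follow-up continued to day 90.*
2. In Protocol 4.10.3.3, record for both arms the date and reason of each dressing lift or replacement.
3. Summarise these by arm within SAP 8.7.7.

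Leave the SOC replacement rule and the primary analysis as they are.

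**Cost.** One protocol sentence, a date and a reason field on the case report form where not already present, and extra rows in an existing summary. The clinical downside is a brief loss of negative pressure and of the closed environment, plus a replacement dressing, in what should be few ciNPT subjects inspected early.
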